4.1.1.2 Progression-free Survival Time

Progression-free survival time will be defined as the number of days from the date of first dose to the date of earliest disease progression based on RECIST v1.1 and irRECIST, or to the date of death, if disease progression does not occur.

CONFIDENTIAL

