#### **2.2.3.2 Progression-free Survival Time**

Median PFS time evaluated using RECIST v1.1 and irRECIST criteria is a Phase 1 and Phase 2 secondary endpoint.

PFS time will be defined as the number of days from the date of first dose to the date of earliest disease progression based on radiological or clinical assessment or to the date of death, if disease progression does not occur. Every effort will be made to follow subjects for PFS if they complete or discontinue the study prior to progression.

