## **3.3 Analysis Variables**

### **3.3.1 Clinical Efficacy**

Tumor response will be assessed using RECIST v1.1 and irRECIST criteria. When a radiological assessment is unavailable to determine RECIST (irRECIST), a clinical assessment of progressive disease and/or death may be used in lieu of the RECIST (irRECIST) to determine disease response. This combined clinical efficacy endpoint will be used in the primary efficacy analysis. RECIST and irRECIST criteria are described in detail in the protocol, and an abbreviated description is provided below.

RECIST evaluation of target lesions are as follows:

Response	Criteria for Response
Complete Response (CR)	Disappearance of all target lesions
Partial Response (PR)	At least a 30% decrease in the sum of the diameters of target lesions taking as reference the baseline sum diameters
Stable Disease (SD)	Neither sufficient shrinkage to qualify for PR nor sufficient increase to qualify for PD
Progressive Disease (PD)	At least 20% increase in the sum of the diameters of target lesions taking as reference the baseline sum diameters or new lesion identification

irRECIST evaluation of target and new lesions are as follows:

Complete Response (irCR)	Complete disappearance of all target and new, measurable lesions, with the exceptions of lymph nodes which must decrease to < 10 mm in short axis.
Partial Response (irPR)	Decrease in TMTB* $\geq$ 30% relative to baseline.
Stable Disease (irSD)	Not meeting criteria for irCR or irPR, in absence of irPD.
Progressive Disease (irPD)	Increase in TMTB $\geq$ 20% relative to nadir.

\*TMTB = SumD target lesions + SumD new, measurable lesions.

For both RECIST and irRECIST, if CA125 levels are initially above the upper normal limit, they must normalize for a subject to be considered in complete clinical response.

Efficacy variables include:

- Progression-free Survival
  - Proportion of subjects surviving without progression at 6 months (based on RECIST v1.1 and/or clinical progression/death) – Phase 2 primary endpoint
  - Proportion of subjects surviving without progression at 6 months (based on irRECIST and/or clinical progression/death) – Phase 2 secondary endpoint
  - Proportion of subjects surviving without progression at 12 months (based on RECIST v1.1 and irRECIST and/or clinical progression/death) – Phase 2 secondary endpoints

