### **3.8 Efficacy Analysis**

#### **3.8.1 Progression-free Survival**

The primary endpoint in Phase 2 of this study is the PFS rate at 6 months defined as the visit at the start of Cycle 7, where progression is assessed for subjects based on a combination of RECIST v1.1 and/or the clinician's assessment of clinical progression or death. The primary efficacy analysis will be based on the Per Protocol population. A sensitivity analysis will be conducted on the ITT population. A secondary efficacy analysis will be conducted on the Phase 2 Per Protocol population.

The primary efficacy analysis entails testing the null hypothesis that PFS at 6 months is less than or equal to 25% against the alternative hypothesis that PFS at 6 months is higher for those treated with PLD and MEDI4736 combination. This hypothesis will be tested at  $\alpha=0.05$  using the 90% two-sided confidence interval for the PFS rate at 6 months based on Kaplan-Meier product limit estimates. The null hypothesis will be rejected in favor of the alternative if the lower bound of that confidence interval is greater than 25%. The null hypothesis will also be tested using a one-sided binomial test as a sensitivity analysis. In this analysis, if a subject has no tumor response assessment, or discontinued treatment or withdrew from the study for other reasons, he or she will be considered as "progressed." The null hypothesis will be rejected in favor of the alternative if the lower bound of a two-sided 90% binominal confidence interval is greater than 25%.

Table displays will include PFS rate at 6 months and the corresponding 90% confidence interval along with the corresponding number of subjects at risk. In addition, PFS will be presented graphically.

Secondary efficacy analyses will use the secondary efficacy endpoints listed in section 3.3.1 of the SAP and will be based on the ITT population. PFS rate and the corresponding 95% confidence interval will be calculated based on Kaplan-Meier product limit estimates and will be displayed by cohort and phase.

Descriptive analyses of PFS will include the following:

- Number and percentage of subjects that died or had a confirmed progression,
- Number and percentage of subjects that survived without a confirmed progression,
- Number and percentage of subjects lost to follow up (unknown survival and/or progression status), and
- Number of subjects missing the tumor response assessment

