PFS time will be summarized for each cohort and phase and will include the 25th percentile, median, 75th percentile, corresponding 95% CIs, minimum and maximum, where PFS time will be calculated using the Kaplan-Meier method. In addition, PFS will be presented graphically.

PFS time is defined as time from the start date of the treatment (Day 1) to the first occurrence of confirmed progression (clinical or radiological), or the date of death due to any cause, whichever occurs first. Subjects without documentation of progression at the time of the analysis will be censored at the date of the last tumor response assessment, date of start of alternate therapy, or last contact if in post study follow-up, whichever comes first. Subjects with no tumor response assessment will be censored at the start date of the treatment.

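### SAP 3.8.1 runs PFS to an undefined *confirmed* progression, against the *earliest* progression used elsewhere, and its censoring rule leaves a single documented RECIST progression without a status

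*SAP*

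**What the plan says.** SAP 3.8.1 runs PFS time from the start of treatment "to the first occurrence of confirmed progression (clinical or radiological", or to death if that comes first. Its descriptive counts carry the same qualifier: "Number and percentage of subjects that died or had a confirmed progression" and "Number and percentage of subjects that survived without a confirmed progression". The censoring sentence that follows the event definition uses a different word: "Subjects without documentation of progression at the time of the analysis will be censored at the date of the last tumor response assessment", or at the start of alternate therapy or at last post-study contact if that is earlier.

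Other places define the same endpoint without the qualifier. Protocol 4.1.1.2 uses "the date of earliest disease progression based on RECIST v1.1 and irRECIST". SAP 2.2.3.2 uses the "date of earliest disease progression based on radiological or clinical assessment or to the date of death". SAP 3.3.1 builds the endpoint from RECIST 1.1, with clinical progression or death where no scan is available, and states: "This combined clinical efficacy endpoint will be used in the primary efficacy analysis". The opening paragraph of SAP 3.8.1 describes the primary endpoint in the same terms.

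The primary test rejects a 6-month PFS rate of 25% or less if the lower limit of the two-sided 90% Kaplan-Meier interval exceeds 25%. A binomial sensitivity analysis counts some subjects as progressed by rule: "In this analysis, if a subject has no tumor response assessment, or discontinued treatment or withdrew from the study for other reasons".

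**The concern.** A Kaplan-Meier test needs an event time or a censoring time for every subject, and the closing paragraph of SAP 3.8.1 is the only place where the SAP gives both in detail. That paragraph uses *confirmed* for the event and *documentation* for censoring, and the two are not complements. A living subject with one documented RECIST progression who then leaves fails the event sentence and also falls outside the censoring sentence. The descriptive counts would list her as surviving without a confirmed progression. The censoring sentence also literally covers a subject who died without documented progression, although that death is an event.

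The programmer must therefore decide what happens to an observed progression in an open-label, single-arm trial with one primary test. Counting it as an event follows the protocol. Dropping it, censoring it, or moving it to a later confirmation date raises the estimated 6-month rate.

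**Working it through.** **1. Is *confirmed* defined anywhere?**
- Target-lesion progression under RECIST 1.1 (Protocol 8.5.3.1) rests on one assessment against the smallest sum. No repeat scan is required.
- Protocol 8.5.3.2 provides for later review only in the exceptional case of clear progression confined to non-target lesions.
- The only repeat-imaging rule is in Protocol 8.6: under irRECIST, progression at or before 12 weeks is confirmed by imaging at least 4 weeks later. Protocol 8.6 presents this as a key difference from RECIST 1.1. The Day 85 scan is 84 days after Day 1, exactly at that limit, and has a ±3-day window, so some first scans fall inside the rule and some outside. The Day 169 scan is outside.
- No procedure exists for confirming clinical progression, although the event sentence applies the word to it.
- Protocol 3.1.10.1 separates meeting RECIST 1.1 progression from its later confirmation, and Protocol 3.1.10 ties treatment withdrawal to confirmation by irRECIST. In this trial, confirmation can therefore mean a separate later step.

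**2. The plan's own figure.** Protocol 3.1.6 gives n = 41, 25% against 45%, one-sided alpha 0.05, exact test, 80% power. The exact binomial rule is success at 16 or more of 41: alpha 0.033, power 0.823. (At 15 or more, alpha is 0.067.) The sample size reproduces. The relevant boundary case is therefore 15 of 41.

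**3. Illustration of the censoring branch.** Assumptions, none of them from the documents: all progressions are seen at the Day 85 or Day 169 scan; 16 subjects progress at Day 85; c of these are treated as unconfirmed and censored at that scan; every Day 169 progression is counted.

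With d₁ = 16 − c events among 41, and d₂ events among the 25 still at risk at Day 169:

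S = (1 − d₁/41)(1 − d₂/25)

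Greenwood sum g = d₁/[41(41 − d₁)] + d₂/[25(25 − d₂)]

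Plain lower limit = S − 1.645·S·√g

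Log-log lower limit = exp(−exp(ln(−ln S) + 1.645·√g/|ln S|))

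For 15 progression-free (d₂ = 10):
- c = 0: S = 15/41 = 0.366; g = 0.01561 + 0.02667 = 0.04228.
- c = 1: S = (26/41)(15/25) = 0.380; g = 0.01407 + 0.02667 = 0.04074.

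| Progression-free | Day 85 / Day 169 progressions | Censored at Day 85 | S | Lower limit, plain / log-log | Reject 25%? |
|---|---|---|---|---|---|
| 15 | 16 / 10 | 0 | 36.6% | 24.2% / 24.5% | no |
| 15 | 16 / 10 | 1 | 38.0% | 25.4% / 25.6% | yes |
| 14 | 16 / 11 | 0 | 34.1% | 22.0% / 22.4% | no |
| 14 | 16 / 11 | 1 | 35.5% | 23.1% / 23.4% | no |
| 14 | 16 / 11 | 2 | 36.9% | 24.1% / 24.4% | no |
| 14 | 16 / 11 | 3 | 38.2% | 25.2% / 25.4% | yes |

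With 15 progression-free and one censored, the splits 13/13, 15/11 and 18/8 give lower limits of 25.3–25.7%, so the decision is the same. If the censored subject also left treatment, the binomial sensitivity analysis stays at 15/41 (exact lower limit 24.1%, not rejected) and would disagree with the primary analysis.

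**4. Illustration of the dating branch.** Suppose events were dated at a confirmation at least 4 weeks later, an interval borrowed from irRECIST. A progression first seen on Day 169 would then be dated Day 197 or later and leave the 6-month count. If 5% of subjects first progress at that scan (assumed), a true 25% would appear as 30%, and the exact chance of 16 or more of 41 would rise from 0.033 to 0.14.

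**The case against.** The strongest reply is that *confirmed* simply means documented. The parenthesis covering clinical and radiological progression fits that reading, as does the word *documentation* in the next sentence. SAP 2.2.3.2, SAP 3.3.1 and the opening of SAP 3.8.1 all describe the endpoint without confirmation. That reading reconciles every passage and produces no bias. It is the more likely intention, but the text does not settle it, because the protocol elsewhere treats confirmation as a separate later step.

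A reader might infer that the SAP instructs unconfirmed progressions to be censored, so that the primary test is anti-conservative as written. The documents do not support this. The censoring sentence does not reach a subject with a documented progression, so censoring her is an added step; the literal text leaves a gap.

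A reader might also want to quote an inflated type I error. That is not supported either, since every unconfirmed share has to be assumed and the answer depends on where it is placed. At a true rate of 25%, a 2% share at Day 85 only gives 4.2–4.8%, still below 5%. A 10% share gives 6.6–11.9% if confined to Day 85, and about 16–17% if applied at both scans.

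Several features limit the exposure. On-study follow-up imaging continues 84 days after the last assessment (flowcharts in Protocol 3.2). Treatment may continue until confirmation (Protocol 3.1.10.1), so some first progressions will be confirmed. Progression dates are collected after the study (Protocol 3.1.16). Deaths are events. The binomial analysis counts many leavers as progressed. These points stand, but they do not close the gap. Continuing past progression is optional, subjects who start other anti-cancer therapy go off-study (Protocol 3.1.10), collecting a date does not say which date is the event, and the binomial analysis neither mentions unconfirmed progression nor drives the primary decision.

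Finally, the one-subject reversal needs exactly 15 of 41, which has probability 3.3% at a true rate of 25% and 7.1% at 45%. That is correct; the example shows sensitivity at the boundary and is not a forecast.

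**Conclusion.** The conflict in wording is certain. SAP 3.8.1 uses an event that differs from Protocol 4.1.1.2, from SAP 2.2.3.2 and from the primary-endpoint wording in SAP 3.3.1 and 3.8.1 itself. It does not define the qualifier for RECIST 1.1 or clinical progression, and its event and censoring sentences do not cover every subject. This should be corrected, because it concerns the event definition of the primary test.

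The bias is conditional. It is nil if *confirmed* means documented. It is upward if documented RECIST progressions are dropped, censored or dated at a later confirmation. Its size cannot be derived from the documents. The reversals with one subject at 15/41 and three at 14/41 rest on the assumed scan pattern and on a censoring step that the SAP does not state.

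**What to change.** In SAP 3.8.1:
- For RECIST 1.1 PFS, define the event as the first documented progression (radiological, or clinical where no scan is available) or death, dated at first documentation.
- Remove *confirmed* from that event and from the descriptive counts.
- State that a documented RECIST progression followed by departure or new therapy is an event at the progression date, and censor only subjects with neither progression nor death.
- Limit confirmation to irRECIST PFS as in Protocol 8.6, and state whether a confirmed irRECIST progression is dated at first detection or at confirmation.

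The cost is SAP wording and dataset derivation only. The data are already collected, and the planned test (16 or more of 41 in the exact calculation, alpha 0.033, power 0.823) is unchanged.

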3.1.10 Subject Withdrawal from Treatment or Study

A subject will be **withdrawn from study treatment** for any of the following reasons:

1. Withdrawal of consent for further treatment.
2. Pregnancy or intent to become pregnant.
3. Dose-limiting toxicity at any time (see Section 3.1.9 for definition of DLT and permitted continuation).
4. Confirmation of progressive disease by irRECIST criteria requiring alternative treatment.
5. Significant protocol violation or noncompliance that, in the opinion of the Investigator or Sponsor, warrants withdrawal.
6. Development of intercurrent, non-cancer related illnesses or complications that prevent either continuation of therapy or regular follow-up.
7. Best medical interest of the subject (at the discretion of the Investigator)

Discontinuation from receiving study treatment does not mean that the subject is withdrawn from the study. If feasible, subjects who are withdrawn from study treatment should enter the On Study Follow-Up, followed by the Post Study Follow-up (see Sections 3.1.16 and 3.2).

Subjects who begin other anti-cancer therapy should immediately be considered off-study and proceed to the Post Study Follow-up (see Section 3.1.16).

A subject will be **withdrawn from the study** for the following reasons:

1. Best medical interest of the subject at the discretion of the Investigator.
2. Initiation of alternative anti-cancer therapy including marketed or another investigational agent.
3. Withdrawal of consent for all follow-up.
4. Lost to follow-up.
5. Death

General subject withdrawal criteria are outlined in the Administrative, Legal and Ethical Requirements section of the protocol (see Section 7.2.6).

See also Sections 8.2, 8.3, and 8.4 for subject withdrawal from treatment due to necessary dosing interruptions or discontinuations.

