3.1.16 On Study and Post Study Follow-up

All subjects, whether they complete the study as planned, discontinue treatment prematurely, or withdraw from the study as per Section 3.1.10, will be followed as per institutional guidelines in accordance with the usual standard of care principles.

For all subjects who complete study treatment or discontinue treatment prematurely, there will be an On Study Follow-up Period (see Section 3.2) for 90 days after the last study drug administration, which will include collection of AE data (see Section 7.1.5 for details on collection of AEs).

If the determination is made to remove a subject from treatment at a visit that coincides with the first visit of the On Study Follow-up Period, any assessments required in the first On Study Follow-up visit that are not covered as part of the last on-treatment visit (usually correlative labs) should be done as soon as possible. If these assessments cannot be done on the same day, the subject should be brought back in at the earliest opportunity. Any assessments or correlative samples required by both the last on-treatment visit and the first On Study Follow-up visit should not be repeated.

Following the On Study Follow-up, there will be a Post Study Follow-up, where clinical outcomes data (dates of progression/relapse and survival) will be collected every 3 months for 3 years from initiation of treatment.

The Post Study Follow-up will include a query to determine if there were any immune-related adverse events (irAEs) during the 90 days since the last administration of study drug.

For subjects who do not continue Post Study Follow-up at one of the study sites after the end of study, the Principal Investigator, or the clinical team under the supervision of the Principal Investigator, will obtain this data through review of outside records or communication with the subject or his/her physician.

See Section 3.1.12 for optional study treatment extension.

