4.1.2 Subject Evaluation & Statistics

The Per-Protocol (PP) Population for clinical efficacy is defined as all subjects who received at least 75% of the scheduled doses of MEDI4736, motolimod (pre Amendment 2), and PLD over the first 2 cycles, as well as respective disease assessments, without major protocol violations. The Intent-To-Treat (ITT) Population for clinical efficacy is defined as all subjects who receive at least one dose of PLD, motolimod (pre Amendment 2) or MEDI4736.

The analysis of clinical efficacy will be based on both the intent-to-treat (ITT) and the per-protocol (PP) populations.

The PFS Rate at 6 months based on RECIST v1.1 evaluated for the per-protocol analysis population constitutes the primary endpoint in Phase 2 of the study. This PFS rate along with its one sided 95% Confidence Interval (CI) based on binomial distribution will be estimated and reported. The one-sided null hypothesis of 6-month PFS ≤ 0.25 will be rejected at 0.05 level of significance if the 95% one-sided CI does not contain 0.25. The 12-months PFS rate along with its 95% one-sided CI will be calculated and reported as a secondary endpoint.

Tumor Response will be summarized and analyzed descriptively for each cohort and analysis population. A 95% Confidence Interval based on binomial distribution will be constructed for the estimated ORR.

Median OS will be calculated using the Kaplan-Meier method. The analysis of PFS and OS will be updated based on data collected during the Post Study Follow-up (see Section 3.1.16).

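### SAP 3.8.1 censors at alternate therapy only if no progression is on record at analysis, so a subject who switches before 6 months and progresses after Day 169 counts as event-free in the primary Kaplan-Meier test

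*SAP*

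**What the plan says.** SAP 3.8.1 dates the PFS event at the "first occurrence of confirmed progression (clinical or radiological), or the date of death due to any cause, whichever occurs first". Nothing in that definition stops the clock at a new therapy.

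The next sentence handles censoring: "Subjects without documentation of progression at the time of the analysis will be censored at the date of the last tumor response assessment", followed by two alternatives, "date of start of alternate therapy, or last contact if in post study follow-up, whichever comes first". All three dates sit under the same opening condition.

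The primary test, in the same section, is made "using the 90% two-sided confidence interval for the PFS rate at 6 months based on Kaplan-Meier product limit estimates". The null hypothesis is rejected if the lower limit is above 25%. Six months is the start of Cycle 7, target Day 169 in the flowchart.

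Protocol 3.1.10 deals with switching: "Subjects who begin other anti-cancer therapy should immediately be considered off-study and proceed to the Post Study Follow-up". Under Protocol 3.1.16, in that follow-up, "clinical outcomes data (dates of progression/relapse and survival) will be collected every 3 months for 3 years from initiation of treatment". Protocol 4.1.2 adds: "The analysis of PFS and OS will be updated based on data collected during the Post Study Follow-up".

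SAP 3.8.1 also plans a binomial sensitivity analysis. There, if a subject has no tumor assessment, or "discontinued treatment or withdrew from the study for other reasons, he or she will be considered as" progressed.

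**The concern.** Kaplan-Meier estimation requires that whether a subject is censored at a given time does not depend on what happens to her afterwards. Here it does. Of two subjects with the same stable scan and the same Month 4 switch, one is kept at risk through Day 169 because she progressed in Month 9. The other is censored at her last scan because she had not progressed when the data were cut. A later cut can move subjects from the second group to the first, so the 6-month rate can change although nothing before 6 months has changed.

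For subjects whose progression comes after Day 169, time on a non-study drug is credited to PLD plus MEDI4736. In a single-arm trial judged against a fixed 25%, that can affect the stated conclusion.

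**Working it through.** **Does the route exist?**

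1. A subject has stable disease at the Day 85 scan (Cycle 4), stops, and starts another agent in Month 4. Protocol 3.1.10 moves her to Post Study Follow-up.
2. Progression dates are still collected there (Protocol 3.1.16) and feed the PFS analysis (Protocol 4.1.2).
3. The dose criterion of the Per-Protocol Population covers only the first 2 cycles (SAP 3.2.2), so a Month 4 switch does not by itself remove her.

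**What SAP 3.8.1 does with her**

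| What happens after the switch | Treatment as written |
|---|---|
| Progression documented after Day 169 | Event at that date; event-free at 6 months |
| Progression documented between switch and Day 169 | Event before 6 months |
| No progression or death by the analysis | Censored at the earliest listed date, no later than the switch |
| Death without documented progression | Conflict: the definition makes it an event; the censoring sentence looks only at progression |

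**The plan's own figure.** Protocol 3.1.6 plans 41 evaluable subjects for 80% power, 25% against 45%, one-sided 0.05, exact test. The exact rule is at least 16 of 41 progression-free: alpha 0.0333, power 0.8225. The planned size reproduces.

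**Size, on assumed counts.** Take N = 41 with 18 events at Day 85, 3 switchers (stable at Day 85, progressing after Day 169), 7 events at Day 169 and 13 event-free on study treatment. S is the product of (1 − d/n), and V is the Greenwood sum of d/[n(n − d)]. The plain 90% lower limit is S(1 − 1.645√V); the log-log limit is S raised to exp(1.645√V/|ln S|). The SAP names no transformation, so both are shown.

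- *As written:* S = (23/41)(16/23) = 16/41 = 39.0%. V = 18/(41×23) + 7/(23×16) = 0.0381. Lower limit 26.5% plain, 26.6% log-log: rejected.
- *All three censored at Day 85:* S = (23/41)(13/20) = 36.5%. V = 18/(41×23) + 7/(20×13) = 0.0460. Lower limit 23.6% or 23.9%: not rejected.
- *All three counted as progressed:* 13/41 = 31.7%.

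Keeping 18 and 7 events and varying the number of switchers among the 16 who are event-free as written:

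| Switchers | As written | Censored at Day 85 | Difference (points) | Lower limit if censored (plain / log-log) |
|---|---|---|---|---|
| 2 | 39.0% | 37.4% | 1.6 | 24.7% / 24.9% |
| 3 | 39.0% | 36.5% | 2.5 | 23.6% / 23.9% |
| 4 | 39.0% | 35.4% | 3.6 | 22.4% / 22.8% |

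A second assumed layout (15 events at Day 84, 12 event-free on study treatment, switches at Day 110, the rest progressing at Day 169) gives 34.1% against 31.7% with 2 switchers and 39.0% against 34.6% with 4: gaps of about 2 and 4 points.

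**The opposite direction.** Let the 3 switchers progress at Day 140 instead, with 6 events at Day 169 and 14 event-free. As written, S = (23/41)(20/23)(14/20) = 34.1%, lower limit 22.0% or 22.4%: not rejected. Censoring at the switch gives S = (23/41)(14/20) = 39.3%, lower limit 26.3% or 26.4%: rejected.

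**The case against.** The best defence has four parts.

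- **Intent.** By naming alternate therapy as a censoring date, the SAP evidently means to censor there; this is loose wording, not a decision to credit other drugs. That is fair, and it is why the fix follows the SAP's own choice. The wording still governs the derivation.
- **The sensitivity analysis.** The binomial analysis counts subjects who discontinued or withdrew as progressed, which is stricter than censoring (31.7% against 36.5% in the example), and would expose the problem. The protocol's own primary test (3.1.6, 4.1.2) is also binomial. This mitigates the problem, but the SAP's deciding test is the Kaplan-Meier one.
- **A narrow route.** It needs a switch without progression before Day 169 and progression documented only afterwards. Under Protocol 3.1.10, stopping treatment is not leaving the study, and imaging continues in On Study Follow-up. This limits the number affected, which the documents do not give.
- **Counts at the decision edge.** With 18 Day 85 events and 3 switchers, varying the number event-free on study treatment from 8 to 19 changes the decision at one value only, 13. With 2 or 4 switchers there is again one such value; with 1 there is none. The examples show that a change of decision is possible, not that it is likely.

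A reader might also infer that every switcher counts as a 6-month success, that deaths after a switch do too, or that the bias is always favourable. The documents support none of these. Switchers without progression or death are censored, progression before Day 169 is an event, the handling of death is contradictory, and the effect is favourable only for progression after Day 169.

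**Conclusion.** The censoring rule is wrong as written and should be corrected before the primary analysis. For switchers whose progression is documented after Day 169, the primary Kaplan-Meier analysis keeps them event-free at 6 months, while otherwise identical switchers are censored according to later outcome and data cut. This group raises the 6-month rate, by about 2 to 4 points for 2 to 4 such subjects of 41. That size rests on assumed counts, on stable Day 85 scans before the switch, and on a literal reading of the opening condition. Whether the trial's decision would change cannot be told from the documents. The handling of death without documented progression also needs to be settled.

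**What to change.** In SAP 3.8.1, replace the condition for switchers with: *Subjects who start alternate anti-cancer therapy before progression or death will be censored at the last tumor assessment on or before that start date, regardless of later progression or death.* Apply it to the RECIST and irRECIST PFS rates and times. This also settles the conflict over deaths after a switch.

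Add a sensitivity analysis that counts all later progressions and deaths as events for every subject, and keep the existing binomial analysis beside it.

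The cost is one sentence, one derivation flag and one further analysis; the therapy start date is already needed for the existing rule. State the downside in the SAP: progressions and deaths between the switch and 6 months become censored, so the rate can rise as well as fall, and censoring at a switch may be informative. The two sensitivity analyses show how much this matters.

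### PFS censoring discards progression-free post-study contacts but counts events learned at them, which can lower mainly the secondary 12-month PFS rate

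*SAP*

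**What the plan says.** **Events.** SAP 3.8.1 ends PFS time at the "first occurrence of confirmed progression (clinical or radiological), or the date of death due to any cause, whichever occurs first". It sets no limit by data source or by time since the last scan.

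**Censoring.** The same section censors subjects without documented progression as follows: "date of the last tumor response assessment, date of start of alternate therapy, or last contact if in post study follow-up, whichever comes first". It adds: "Subjects with no tumor response assessment will be censored at the start date of the treatment".

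**Post-study data.** Protocol 3.1.16 places Post Study Follow-up after the 90-day On Study Follow-up; in it, "clinical outcomes data (dates of progression/relapse and survival) will be collected every 3 months for 3 years from initiation of treatment". Protocol 4.1.2 says: "The analysis of PFS and OS will be updated based on data collected during the Post Study Follow-up". SAP 2.2.3.2 states the intent: "Every effort will be made to follow subjects for PFS if they complete or discontinue the study prior to progression". Some subjects arrive early: "Subjects who begin other anti-cancer therapy should immediately be considered off-study and proceed to the Post Study Follow-up" (Protocol 3.1.10).

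**For comparison.** SAP 3.8.3 censors overall survival at the last contact. In SAP 3.8.1 the 6-month primary analysis uses Kaplan-Meier. Its binomial sensitivity analysis counts subjects who discontinue or have no assessment as progressed, so it does not use the censoring rule.

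**The concern.** The last-contact term was evidently written for subjects in Post Study Follow-up, but taking the earliest date stops it from ever being chosen. One contact then has two different effects. If the subject has progressed or died, the event enters at its later date and she stays in the risk set until then. If she is progression-free, the contact adds nothing and she is censored back at her last scan. Censoring therefore depends on the later outcome, which breaks the non-informative censoring that Kaplan-Meier needs. Beyond a subject's own last scan, only those who go on to have an event are credited with time. A programmer must either apply the sentence literally or guess that last contact was meant to replace last scan, and the two give different results.

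**Working it through.** **1. Can last contact be the earliest date?** A scan is a contact, so last contact ≥ last scan, and the earliest-date rule never selects last contact except in a tie. Subjects with no scan go to Day 1 under their own sentence. The term has no case left to apply to.

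**2. Calendar at 12 months (four-weekly schedule, Protocol 3.2).** Scans fall on Days 85, 169 and 253, then 84 days later: 253 + 84 = Day 337. The next would be 337 + 84 = Day 421. Last dose is Day 311, so On Study Follow-up ends at 311 + 90 = Day 401. A completer on schedule who does not enter the extension has her last protocol scan near Day 337. If later contacts show her progression-free, she is still censored there, before Day 365.

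**3. Worked example (illustrative, 41 subjects).** Ten progress at Day 85, leaving 31. Eight then leave scanning: four progress at Day 130, known from contacts, and four are progression-free at a Day 200 contact. Of the other 23, nine progress at Day 169.
- Rule as written: 31/41 × 23/27 × 14/23 = 0.392.
- Censoring at last progression-free contact: 31/41 × 27/31 × 18/27 = 0.439, which equals the observed 18/41.

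**4. Design figure.** The plan gives no figure for this rule. Its sample size does reproduce: 0.25 versus 0.45, one-sided 0.05, exact binomial, n = 41 rejects at 16 or more progression-free, with alpha 0.0333 and power 0.8225.

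**5. Size by simulation.** From the documents: N = 41, 24-month enrollment, scans every 84 days until 90 days after last dose, then contacts. Assumed, because the documents do not give them: exponential PFS, 10-30% stopping without progression per 12 weeks, and a data cut-off 6 to 15 months after the last start. With a true 6-month rate of 0.45, the true 12-month rate is 0.45^(365/183) = 0.203.
- 12 months, no extension uptake: 0.148 to 0.189 as written, against 0.197 to 0.204 when censoring at last progression-free contact. The shortfall against truth is 0.203 − 0.189 = 1.4 points to 0.203 − 0.148 = 5.5 points.
- 6 months: the two rules differ by about 0 to 1.6 points, and both mostly sit at or above 0.45. With 20% stopping and a 6-month cut-off, for example, they give 0.462 and 0.471.
- With a true 6-month rate of 25% and cut-offs at 6 or 12 months, the 12-month gap between rules is 0.2 to 1.4 points on about 7%.
- Once every subject has 3 years of follow-up the difference is negligible.

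**The case against.** **The primary endpoint.** A reader might infer that the rule biases the 6-month PFS rate low. The calculations do not support that. Progression is dated at scheduled scans, which pushes both estimates up, and this mostly outweighs the censoring effect. Few subjects are exposed, because scans continue for 90 days after the last dose: a subject dosed at Cycle 4 still gets the Day 169 scan. This part of the objection stands.

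**The risk set.** A reader might also infer that, once protocol scans end, the risk set holds only subjects who will have an event. It also holds everyone still being scanned. The statement is true only of subjects past their own last scan.

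**The 12-month size.** The gap between two rules is not error against truth. In one scenario the rates were 0.182 as written and 0.215 under last-contact censoring, against 0.203, so 1.2 of the 3.3 points are the alternative overshooting. Under another set of leaving assumptions (30% leaving before Day 168, 90 days of further scans) they were 0.202 and 0.221, so the written rule was close to truth. With 80% of completers entering the extension and a 15-month cut-off, the written rule gave 0.187 to 0.209. Outside imaging could also move the last-assessment date later. These points stand as limits on size.

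**Last-scan censoring is legitimate.** Contact-based status is weaker than a scan, and crediting it raises PFS in an open-label single-arm trial. That is fair, but last-scan censoring is coherent only if events first learned after scanning ends are excluded too, and the SAP counts them.

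**Conclusion.** The point holds as an inconsistency between the event and censoring rules. The last-contact term is inoperative, and Kaplan-Meier PFS falls too fast after a subject's own last scan. The effect falls mainly on the secondary 12-month rate: roughly 1 to 5 points low on about 20% (1.4 to 5.5 across the runs). That range rests on the assumed stopping rate, a true 6-month rate of 45%, no extension uptake and a cut-off 6 to 15 months after the last start. It shrinks with extension uptake and disappears with full 3-year follow-up, but SAP 3.8.1 analyses whatever is known at the time of analysis and fixes no minimum follow-up. The documents do not support extending the claim to the primary 6-month result, and the binomial sensitivity analysis is unaffected. The change is worth making because the repair is cheap, not because the primary conclusion is at risk.

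**What to change.** Use one consistent rule for events and censoring in SAP 3.8.1. Censor event-free subjects at the last date on which progression-free status was documented: the last tumor assessment or, in Post Study Follow-up, the last contact recording no progression. Use the start of alternate therapy instead if it is earlier, and state whether events after that start count.

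At each existing 3-monthly contact, record the date to which the subject is known progression-free and the start date of any new therapy. Protocol 3.1.16 names only progression/relapse and survival dates.

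As a sensitivity analysis, censor at the last tumor assessment and also exclude events first documented after two missed scheduled scans.

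The cost is a short SAP rewording and two fields on contacts already planned. The downside is reliance on contact-based status, which is weaker evidence than a scan; the sensitivity analysis addresses that.
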